**Proprietary confidential information.**

**© 2016 Boehringer Ingelheim International GmbH or one or more of its affiliated companies. All rights reserved.**

This document may not - in full or in part - be passed on, reproduced, published or otherwise used without prior written permission.

Clinical disease status will be assessed at screening, at the administration of the first and the last of the 4 infusions and 3 weeks after the last infusion of a respective course with physical examination, clinical assessment of the B-NHL, and blood samples. CT scans in this trial will be performed in accordance with published guidelines for response evaluation in lymphoma ([R04-1585](#)) and correspond to the use in clinical practice ([section 5.1.2.2](#)). A CT scan will be done prior to treatment (may be performed up to 8 weeks (preferably 4 weeks) prior to first infusion), after 2 courses of treatment, (*i.e.* at week 13 +/- window), and just before the end of treatment (EOT) visit (*i.e.* week 25 +/- window). If the CT scans are not possible or available, magnetic resonance imaging can be used instead. However the same imaging methods should be used consistently throughout the trial. Bone marrow examination, PET scan and additional CT scans will be performed at the discretion of the investigator. Results of CT scan, optional PET scan or bone marrow examination performed during the conduct of the trial should be reported in the eCRF. After the EOT visit which may occur at the latest at week 26, the patient will enter the follow-up phase. During the follow-up phase, disease status evaluations (physical examination, clinical assessment of lymphoma, and blood samples) should be performed at least every 6 weeks until 6 months after the EOT visit, administration of new anti-lymphoma therapy or death, whatever occurs first. More frequent visits may be indicated, *e.g.* for follow-up of laboratory parameters or adverse events which have not been resolved at the EOT visit.

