### 6.2.3 End of treatment and follow-up period

#### 6.2.3.1 End of treatment

The end of treatment (EOT) visit should be performed if patient and investigator refrain from further therapy at any time during the treatment period. For patients who receive course 3 (12 administrations) at the latest 8 weeks after the last administration of BI 836826. If the patient concludes the trial within a treatment course, the information required to be collected at the EOT visit should be obtained as early as possible, preferably immediately. This includes a CT scan, which may be performed if it is considered clinically indicated, *e.g.* to document disease progression. At the EOT visit assessment of all safety and efficacy parameters should be performed according to flowchart for course 3. The status of the patient at EOT has to be documented, *e.g.* in case the patient has progressive disease the date of first documentation of PD has to be recorded. The reason for the completion of active trial treatment or premature discontinuation of trial, if applicable, has to be stated together with date of last administration of the trial drug. If the patient receives other therapy for lymphoma, the therapy has to be stated by name and date of first treatment. For detail see [flowchart](#) for Course 3.

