7.8.1.2 Adverse events

AE analysis will be performed for all treatment periods and selected analyses for the MTD evaluation period.

The analyses of AEs will be descriptive in nature and will follow the standard procedure laid down in the Data Management and Statistics Manual (DM & SM) (including all required tables and listings) (current guideline 'Handling and Summarization of AE Data for CTR and Integrated Summaries' (6)). AEs will be coded with the most recent version of Medical Dictionary for Regulatory Activities (MedDRA). The version number will be displayed as a footnote in the respective tables and listings. The SOC will be sorted alphabetically, and PTs will be sorted by descending frequency of adverse events in the "Total" BI 836826 group

Each patient can be observed during the trial under several doses. Analysing the AE of all treatment courses will be carried out under the initial treatment. No formal statistical analysis is planned for the safety comparison.

The analysis of AEs will be based on the concept of treatment emergent AEs. That means that all AEs occurring between the first administration of BI 836826 until 8 weeks after last administration of BI 836826 will be assigned to the on-treatment period. AEs will be distinguished for the treatment course in which the subjects are on-treatment as well as for screening, and post-study. The actual planned dosage of BI 836826 administered on the day each AE starts will also be derived and will be included in the listing. Listings of screening events will not be sorted by initial treatment. Post-study listings will be sorted by initial treatment.

According to the BI standards, multiple recordings of AEs will be collapsed to episodes on the lowest level term and multiple episodes will be condensed to records on the PT and SOC level. CTCAE grade will be an additional criterion for collapsing and condensing AEs. The maximum CTCAE grade will be assigned to episodes and records. CTCAE grade and DLT information will be displayed in AE listings. MedDRA levels for condensing will be SOC and PT.

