for all analyses. In laboratory listings, the CTCAE grade will be displayed as -1.

Patients with hepatic enzyme elevation will be tabulated.

Patients with possibly clinically significant laboratory values will be tabulated (see [Section 9.2](#)).

The prioritized laboratory values (see [Section 5.4.5.1](#)) will be displayed in Section 15 of the final CTR while all other laboratory parameters will be displayed in the Appendix of the CTR.

Neutropenia, thrombocytopenia and leukopenia

Episodes of low neutrophil, platelet and WBC counts are of special interest. Episodes with CTCAE grade 3/4 as well as episodes with CTCAE grade 4 lasting 7 or more days will be analysed separately.

An episode of low blood counts of grade 4 starts with the first occurrence of a CTCAE grade 4 and lasts until the first time the CTCAE grade falls back to <=3 (analogously for an episode of CTCAE grade 3/4).

In case the episode starts during the EOT or Follow-up, the duration of this episode is defined to be missing. The reason for this approach is that after the EOT laboratory data is only

captured infrequently and therefore the duration of an episode would be overestimated due to lack of data.

If an episode starts before EOT and the CTCAE grade of the respective parameter does not fall back to the respective grade that ends the episode and the patient dies, the end of the episode is defined by the date of death. If the episode starts before EOT and lasts during Follow-up, the episode is censored with the date of DBL.

Number of patients with respective episodes, number of episodes, episodes per patient, duration of individual episode, number of episodes divided by number of infusion per patient, mean and median duration of episode per patient will be displayed.

Additionally, a frequency table displaying number of patients with episode of neutropenia Grade 4 and concomitant AEs in the UDAEC Infections (incl. respiratory infections and sepsis) of any grade as well as only for Grade 3 or 4 infections will be provided. In this context, concomitant AE is defined as AE with onset date within the neutropenia episode. This will be also done for CD4+ T-cell count Grade 4 and concomitant CD4 related specific infections from the UDAEC CD4 related specific infections.

The same way, a frequency table displaying number of patients with episode of thrombocytopenia Grade 4 and concomitant AEs in the UDAEC bleeding of any grade as well as only for Grade 3 or 4 bleeding will be provided.

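### A Grade 4 cytopenia first recorded at or after an early EOT visit is given no duration, so it cannot count as lasting 7 days or more even inside the on-treatment window

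*SAP*

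**What the plan says.** SAP 7.8.2 (neutropenia, thrombocytopenia and leukopenia) singles out prolonged events: "Episodes with CTCAE grade 3/4 as well as episodes with CTCAE grade 4 lasting 7 or more days will be analysed separately". It defines the onset, "An episode of low blood counts of grade 4 starts with the first occurrence of a CTCAE grade 4", and the episode ends when the grade first returns to 3 or below. Three special rules follow.

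- Onset at EOT or later: "In case the episode starts during the EOT or Follow-up, the duration of this episode is defined to be missing". The reason given is that laboratory data are sparse after EOT and the duration would be overestimated.
- Onset before EOT, no recovery, patient dies: "the end of the episode is defined by the date of death".
- Onset before EOT, continuing: "If the episode starts before EOT and lasts during Follow-up, the episode is censored with the date of DBL".

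The timing of EOT is set in the protocol. For a patient who ends within a course, section 6.2.3.1 says that "the information required to be collected at the EOT visit should be obtained as early as possible, preferably immediately". For a patient with 12 infusions, the Course 3 flowchart puts EOT at the latest on day 77±5 of that course, whose last infusion is on day 22.

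The on-treatment period is defined in SAP 7.8.1.2 as "all AEs occurring between the first administration of BI 836826 until 8 weeks after last administration of BI 836826". SAP 7.8.2 applies the same periods to laboratory data, adding the baseline value.

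After EOT, Protocol 6.2.3.2 schedules visits every 6 weeks, or more often if appropriate. Protocol 3.2 foresees extra visits "for follow-up of laboratory parameters or adverse events which have not been resolved at the EOT visit".

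**The concern.** The rule is tied to a visit, and the date of that visit depends on why and when the patient stopped. The earlier the stop, the larger the part of the on-treatment period in which a new episode gets no duration. A Grade 4 neutropenia first seen at an EOT visit a few days after the last infusion is an on-treatment finding by the SAP's own definition, yet it cannot enter the count of episodes lasting 7 days or more or the duration summaries.

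This matters because Protocol 5.2.1.1 excludes haematological events as such from the DLT definition but says that they will be considered when the dose for further development is chosen. The duration of Grade 4 cytopenia is part of that picture. SAP section 3 reports that 3 of the 4 Korean patients at 100 mg had infections associated with Grade 4 neutropenia. A summary whose completeness varies with early stopping is hard to compare across dose cohorts.

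**Working it through.** The plan gives no figure for this analysis that could be reproduced. The check applies its rules to dates.

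**Step 1. Share of the on-treatment window covered by the missing-duration rule.** The window after the last dose is 8 × 7 = 56 days (SAP 7.8.1.2). If EOT falls t days after the last infusion, the days at or after EOT number 56 − t, and the share is (56 − t)/56. The values of t for early stoppers are illustrative.

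| Patient | t (days) | 56 − t | Share |
|---|---|---|---|
| Early stop, EOT next day | 1 | 55 | 98% |
| Early stop | 7 | 49 | 88% |
| Early stop | 14 | 42 | 75% |
| Early stop after 3 weeks of re-evaluation | 21 | 35 | 63% |
| Stop at the end of the 27-day observation in course 1 or 2 | 27 | 29 | 52% |
| 12 infusions, EOT on course 3 day 77 | 77 − 22 = 55 | 1 | 2% |

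For the completer, the ±5-day window gives t = 72 − 22 = 50 (6 days left) to 82 − 22 = 60 (none left).

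**Step 2. The SAP rules applied to example episodes.** Days are counted from the last infusion; duration is end minus start.

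| Onset | EOT | Course | SAP duration | Counted as 7 days or more? |
|---|---|---|---|---|
| 7 | 7 | any | missing | no |
| 10 | 7 | any | missing | no |
| 3 | 21 | resolved day 12 | 12 − 3 = 9 | yes |
| 3 | 7 | unresolved, death day 20 | 20 − 3 = 17 | yes |
| 5 | 7 | not seen to resolve | to database lock | yes |

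In the last row the lock date is not given. With an assumed lock on day 200, 400 or 800, the censored duration is 195, 395 or 795 days.

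**Step 3. The two rules side by side.** Compare the first and last rows. EOT is on day 7 in both, and the counts after EOT can be the same. Onset two days before EOT gives a duration that runs for months; onset on the day of EOT gives none. Both rules face the same sparse data after EOT and treat it in opposite ways. The SAP does not say how a censored duration enters the mean and median per patient.

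**Step 4. A case in which documented time is lost.** Suppose EOT on day 10, with Grade 4 neutrophils that day and again on days 17 and 24. Counting both end days, 24 − 10 + 1 = 15 days are documented (14 without the extra day). The SAP duration is missing, and the episode is not counted as prolonged. This example needs weekly counts after EOT, which the protocol permits but does not schedule.

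**The case against.** The strongest reply is that the rule is narrow and has a stated reason.

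- **It concerns onset, not stopping.** A reader might infer that nobody taken off drug for toxicity can count as having prolonged Grade 4 cytopenia. The documents do not support that. If the cytopenia itself led to the stop, it began before EOT and keeps a duration. Protocol 4.1.4.4 allows up to three weeks of re-evaluation, Protocol 5.2.3.1 asks for at least weekly visits with safety laboratory tests when a course is delayed by an adverse event, and an immediate EOT is only a preference. Many onsets will therefore be recorded before EOT. This stands.
- **The events remain visible.** Only the duration is set to missing. Nothing in SAP 7.8.2 removes these episodes from the episode counts or the Grade 3/4 analysis. The table of Grade 4 neutropenia with concomitant infection has no 7-day threshold, and the worst grade on treatment is reported. This stands.
- **Sparse data are a real problem.** With visits 6 weeks apart, Grade 4 on days 10 and 52 would give 52 − 10 + 1 = 43 days, although the patient may have recovered and relapsed in between. A first-to-last-sample duration is a lower bound only if Grade 4 persisted between samples. This stands, and the fix must limit the gap.
- **The MTD is untouched.** It rests on DLTs in the MTD evaluation period, and all analyses are descriptive. This also stands, but it does not answer the point about the later choice of dose.

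The reply does not explain why the rule should reach far into the on-treatment window for early stoppers and hardly at all for completers, or why the neighbouring rule extends durations to database lock on the same data.

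**Conclusion.** The point holds in a limited form. A Grade 4 cytopenia first recorded at or after an early EOT cannot be classified as lasting 7 days or more, even when it lies within 8 weeks of the last dose and later counts document it. The rule covers about 63% to 98% of the 56-day window for EOT between 21 days and 1 day after the last infusion, against 0 to 6 days for a 12-infusion completer. These shares measure the time exposed to the rule, not the episodes lost.

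Two stronger conclusions are tempting. One is that prolonged cytopenia is under-counted most in the most toxic cohorts. That is not established: the database-lock rule lengthens other episodes in early stoppers, and the net direction is unknown. The other is that 3 of 4, or 75%, of the Korean 100 mg cohort drops out of the count. The documents give neither the onset nor the EOT dates of those episodes, so 0 to 3 are all possible, and zero fits as well as three.

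The number of patients affected cannot be known from the documents. What is established is an uneven and internally inconsistent handling of duration, which the SAP can correct.

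**What to change.** Amend SAP 7.8.2 as follows.

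1. For an episode starting at or after EOT but within 8 weeks of the last dose, derive a minimum documented duration: last minus first consecutive Grade 4 sample, plus 1 day. Link samples only if they lie within a pre-specified maximum gap, for example 14 days. Flag the value as a minimum and count the episode as prolonged if it is 7 days or more.
2. For an episode starting before EOT and unresolved in Follow-up, censor at the last available count instead of the database lock date.
3. Report the number of episodes with missing or minimum duration by dose cohort.

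With a 14-day limit, scheduled 6-week visits (42 days apart) will not be linked, so step 1 recovers time only where extra counts exist. In the day 10 and day 52 example the documented minimum would be 1 day, not 43. Step 3 shows the reader how much remains unknown.

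The cost is a little more wording and programming, with no new data. The prolonged-cytopenia figure may become slightly less favourable.

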3. INTRODUCTION

As per International Conference of Harmonisation, statistical principles for clinical trials, E9 (ICH E9), the purpose of this document is to provide a more technical and detailed elaboration of the principal features of the analyses described in the clinical trial protocol (CTP), and to include detailed procedures for executing the statistical analysis of the primary and secondary variables and other data.

This trial statistical analysis plan (TSAP) assumes familiarity with the protocol, including protocol amendments. In particular, the TSAP is based on the planned analysis specifications as written in CTP Section 7, “Statistical Methods and Determination of Sample Size”. Therefore, TSAP readers may consult the CTP for more background information on the study, e.g., on study objectives, study design and population, treatments, definition of measurements and variables, planning of sample size, randomisation. This TSAP follows the Boehringer Ingelheim (BI) internal reference ([1](#)).

The primary objective of this trial is to determine the maximum tolerated dose (MTD) of BI 836826 in patients with non-Hodgkin lymphoma (NHL) of B-cell origin. BI 836826 is a new biological entity and the maximum planned single dose is 1400 mg. If the MTD is not reached with this dose, an optimal biological dose (OBD) may be defined instead.

The MTD of BI 836826 was defined as 100 mg in this trial for Caucasian patients. This dose was declared based on safety demonstrated during the dose escalation which was performed in 37 Caucasian patients. The results have been reported in the “CTR – Phase I Safety Analysis Report” ([8](#)).

The planned additional expansion phase enrolled 4 patients (all 4 in Korea). After 3 of these 4 Korean patients developed significant toxicities (ie. infections associated with Grade 4 neutropenia), the protocol was amended for the need of exploring lower dose levels (50 mg and 75 mg) in a designated escalation cohort of Korean patients, with the aim of defining a MTD in Korean patients. Thus, the expansion phase on 100 mg had been stopped. Secondary objectives are the collection of overall safety and anti-tumour efficacy data and the determination of the profile of BI 836826.

In the following, study medication always refers to BI 836826.

SAS® Version 9.2 (or higher) will be used for all analyses.

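### The SAP counts a cytopenia episode that is unresolved at death as completed on the death date, so an early death reads as a short episode in the duration summaries

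*SAP*

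**What the plan says.** SAP 7.8.2 (paragraphs on neutropenia, thrombocytopenia and leukopenia) starts a Grade 4 episode at the first Grade 4 value; the episode "lasts until the first time the CTCAE grade falls back to <=3". Grade 3/4 episodes are handled in the same way. Three rules cover episodes without that ordinary ending:

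- Onset before the end-of-treatment (EOT) visit, no recovery, patient dies: "the end of the episode is defined by the date of death".
- Onset before EOT, still running afterwards: "If the episode starts before EOT and lasts during Follow-up, the episode is censored with the date of DBL".
- Onset at EOT or in follow-up: "the duration of this episode is defined to be missing".

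The durations are used in two places. First, "episodes with CTCAE grade 4 lasting 7 or more days will be analysed separately". Second, individual durations are shown and "mean and median duration of episode per patient will be displayed". Nothing in the section flags an episode that was unresolved at death or gives it a category of its own.

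**The concern.** Death prevents recovery; it is not a form of recovery. The SAP uses the language of censoring for episodes that run into follow-up but not for death, so the death date reads as a true end. A patient who dies three days into unrecovered Grade 4 neutropenia then has the same duration as one whose count recovered on that day. Both fall outside the 7-day analysis, and both pull the mean and median down equally.

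Duration matters in this trial. SAP section 3 gives "infections associated with Grade 4 neutropenia" in 3 of the 4 Korean patients as the reason for stopping the 100 mg expansion. Protocol 4.1.4.3 links prolonged neutropenia to the risk of severe infection. Protocol 5.2.1.1 says that haematological events will be weighed when the dose for further development is chosen. A reader of the duration tables should be able to tell a short recovered episode from one cut short by death.

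**Working it through.** The SAP gives no figure to reproduce here, so the check applies its rule directly.

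**Step 1: which deaths leave the 7-day group.** Duration = date of death − date of onset, for onset before EOT and no recovery. The SAP states no day count for episodes, so both versions are shown.

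| Death after onset (days) | Duration | In 7-day group? | Duration with +1 | In 7-day group? |
|---|---|---|---|---|
| 3 | 3 | no | 4 | no |
| 5 | 5 | no | 6 | no |
| 6 | 6 | no | 7 | yes |
| 7 | 7 | yes | 8 | yes |
| 14 | 14 | yes | 15 | yes |

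Only deaths less than about 7 days after onset are affected.

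**Step 2: effect on the summaries (assumed data).** Take seven recovered Grade 4 episodes of 3, 4, 5, 8, 9, 12 and 15 days (sum 56), one per patient. Add patients who die unrecovered 3 days after onset. Percentages are of patients with an episode.

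| Early deaths | 7+ days, SAP rule | 7+ days or died unresolved | Mean (days) | Median (days) |
|---|---|---|---|---|
| 0 | 4/7 = 57.1% | 4/7 = 57.1% | 56/7 = 8.0 | 8.0 |
| 1 | 4/8 = 50.0% | 5/8 = 62.5% | 59/8 = 7.4 | 6.5 |
| 2 | 4/9 = 44.4% | 6/9 = 66.7% | 62/9 = 6.9 | 5.0 |
| 3 | 4/10 = 40.0% | 7/10 = 70.0% | 65/10 = 6.5 | 4.5 |

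More early deaths give shorter summaries.

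**Step 3: a late death works the other way.** Add to the same seven episodes one patient who dies unrecovered at 30 days. The 7-day group becomes 5/8 = 62.5%, the mean (56 + 30)/8 = 10.8 days and the median (8 + 9)/2 = 8.5 days. The rule has no general direction.

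**Step 4: size in a small cohort.** SAP section 7 takes percentages relative to all patients in the set, and SAP 6.1 shows Korean patients as separate dose cohorts. Protocol 3.1 gives these 3 to 6 patients per dose. Classifying one early death differently moves the share by 1/6 = 16.7 to 1/3 = 33.3 percentage points.

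**Step 5: size under a simple model (assumed).** Let recovery and death have constant hazards, with mean recovery time m if nobody died and a share s of episodes ending in death. Then mean duration = m(1 − s), P(7+ days) = exp(−7/[m(1 − s)]), and deaths before day 7 = s × (1 − P). With m = 7 days:

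- s = 10%: mean 6.3 days; P = exp(−1.111) = 32.9%; early deaths 6.7% of episodes; combined row 32.9 + 6.7 = 39.6%.
- s = 20%: mean 5.6 days; P = exp(−1.25) = 28.7%; early deaths 14.3%; combined row 42.9% before rounding the parts.

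The gap between the present row and a combined row is exactly the share of early deaths. The documents do not give that share.

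**The case against.** The case against a larger criticism is strong.

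- **Time to death is a legitimate description.** It records time spent at Grade 4 while alive. This stands: the durations are not wrong, but they are pooled without a label.
- **The direction is not established.** Late deaths with no documented recovery lengthen episodes. Follow-up visits are about six weeks apart and may be by telephone (Protocol 6.2.3.2), and the SAP itself warns that sparse data after EOT overestimate duration. This stands.
- **No decision rule uses duration.** The MTD rests on DLTs (SAP 5.1 and 7.4). A drug-related infection of Grade 3 or higher due to neutropenia is a DLT however long the neutropenia lasted (Protocol 5.2.1.1). The analysis is descriptive. This stands.
- **The patient is not lost from the report.** The episode stays in the episode counts and individual durations. If an infection began during it, the patient also enters the neutropenia table for infections of any grade; a fatal adverse event has its own table (SAP 7.8.1.2). This mostly stands, with two gaps: the restricted infection display, "as well as only for Grade 3 or 4 infections will be provided", omits a Grade 5 infection as worded, and the table of fatal events is not linked to episode duration.
- **Taking fatal episodes out of the pooled durations would bring its own bias.** It would also remove long fatal episodes: in Step 3 the mean would drop from 10.8 back to 8.0 days. This stands and shapes the fix.

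A reader might infer that the rule makes the most lethal cohort look as if it had the mildest cytopenia. The documents do not support that. The available text reports infections with Grade 4 neutropenia in three Korean patients, but not that any of them died, or died within 7 days of onset.

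**Conclusion.** The point holds in a narrow form. Under SAP 7.8.2, an unrecovered Grade 4 episode with onset before EOT and death less than about 7 days later is left out of the 7-day analysis and is indistinguishable from an early recovery in the mean and median. The exact boundary depends on a day count that the SAP does not state. The rule covers death from any cause.

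The actual effect is unknown and may be nil, because the documents do not give the number of such deaths. The Step 2 durations and Step 5 hazards are assumptions that show how the rule behaves; they do not estimate this trial's results. The 17 to 33 points for one early death follow from the planned Korean cohort sizes. The MTD and the DLT counts are untouched. This is a cheap improvement to how safety tables are read, not a fault in the dose-finding analysis.

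**What to change.** In SAP 7.8.2:

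1. Give each episode an outcome code: recovered, unresolved at death, or censored.
2. In the table of Grade 4 episodes of 7 or more days, add two rows: *died with unresolved Grade 4 before day 7* and *7 or more days or died unresolved*. State the day count used, since the first row depends on it.
3. Keep the mean and median over all episodes as planned, and show the number unresolved at death beside them. Do not drop fatal episodes from these summaries.
4. Mark the episodes unresolved at death in the listing of individual durations.

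The dates needed are those the present rule already uses, so no new data are required. The cost is one derived variable, two table rows and a few sentences of SAP text.
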